5.2.5.1 Mini-Mental State Examination (MMSE)

The MMSE (Folstein et al., 1975) is a brief instrument used to assess cognitive function in elderly patients. The range for the total MMSE score is 0 to 30, the sum of each correct answer, with higher scores indicating better cognition. MMSE was collected at baseline under the AIBL protocol and at 12 months under the AV-1451-A08 protocol.

5.2.5.2 Clinical Dementia Rating (CDR) Scale (Berg, 1988)

The CDR examines 6 categories of cognitive functioning domains. Each domain is scored on a scale ranging from 0 to 3 (including 0.5). A CDR Sum of Boxes (CDR-SB) will be generated as the sum of the values in each of the six domains. The CDR-SB sum scores ranges from 0-18, where higher scores indicate greater cognitive impairment. CDR will be collected at baseline under the AIBL protocol and at 12 months under the AV-1451-A08 protocol.

5.2.5.3 Clinically Meaningful Progress

The MMSE and CDR-SB assessments will be dichotomized, to allow for the assessment of risk to progress to a clinically significant change. Subjects will be categorized to these groups by the criteria accordingly.

- MMSE: clinically significant progress is defined as MMSE has a 3 points or more decrease from baseline.
- CDR-SB: clinically significant progress is defined as CDR-SB has a 1 point or more increase from baseline.

5.3 SAFETY ASSESSMENTS

5.3.1 Adverse Events

An adverse event (AE) is any undesirable experience occurring to a subject during a clinical trial, whether or not considered related to the study drug. AEs are classed by severity and seriousness.

Treatment-emergent adverse events (TEAE) are any untoward medical occurrences associated with the use of a drug in humans, whether or not considered drug related. For the purposes of this study, untoward medical occurrences will be considered associated with the use of flortaucipir, and thus be reported as TEAEs if they occur within 48 hours after administration of the PET tracer. The end of study for the purpose of AE reporting is defined as 48 hours after the administration of flortaucipir injection.

The investigator's verbatim term of both serious and non-AEs will be mapped to system organ class (SOC) and preferred terms using the Medical Dictionary for Regulatory Activities (MedDRA) Version 17.0.

Severity is classified as mild/moderate/severe (increasing severity). If a subject reports a TEAE more than once within that SOC/preferred term (PT), the TEAE with the worst case severity will be used in the corresponding severity summaries.

Serious AEs (SAEs) are events that result in one of the following outcomes or constitute one of the following events:

- Death
- Initial or prolonged hospitalization (other than that required by protocol; "social hospitalization" or any hospitalization for non-medical reasons does not constitute an SAE)
- A life-threatening experience (that is, immediate risk of dying)
- Persistent or significant disability/incapacity
- Congenital anomaly/birth defect
- Considered significant by the investigator for any other reason

5.3.2 Vital Signs

Supine blood pressure, pulse rate, and respiratory rate are collected at Screening and two time points – Immediately Prior to (within 5 minutes) Flortaucipir Injection and Prior to Discharge - during the flortaucipir imaging visits. In addition, height is captured at screening, and weight is collected at both Screening and prior to each injection of flortaucipir.

6 STATISTICAL METHODS

6.1 GENERAL METHODOLOGY AND CONVENTIONS

All analysis will be performed using SAS version 9.2 or higher.

Continuous data will be summarized using descriptive statistics (number of subjects [n], mean, standard deviation [SD], median, minimum (min), and maximum (max)). Frequency counts and percentages will be used to summarize discrete variables. Percentages will be rounded to one decimal place, except 100% will be displayed without any decimal places and percentages will not be displayed for zero counts.

The tables and listings will be numbered using a decimal system to reflect main levels of unique tables and listings and sub-levels of replicate tables and the listings with maximum two digits per level (e.g., Table XX.YY.ZZ...). Baseline analysis will be reported in table series 14.1, efficacy analysis in series 14.2, and safety analysis in series 14.3. Listings will be numbered as 16.YY.ZZ.

6.2 DEFINITIONS OF BASELINE AND FOLLOW-UP

Baseline cognitive scores will be collected under the AIBL protocol, outside the AV-1451-A08 electronic data capture (EDC) system. All other baseline data (e.g. demographics) will be reported from data collected from the AV-1451-A08 EDC. All follow-up cognitive scores for the calculation of change from baseline (CFB) are collected under the AV-1451-A08 protocol.

Safety analysis involving CFB calculations for vital signs will consider *Prior to Injection* values as baseline and *Prior to Discharge* as follow-up for each scan session.

6.3 WINDOWS

For all analyses, results will be summarized at the planned study visit they were obtained.

6.4 CALCULATING AGE

Age will be derived in years as the difference between the year of informed consent and year of birth.

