## CONFIDENTIAL

This material is the property of Avid Radiopharmaceuticals (Avid). The information is confidential and is to be used only in connection with matters authorized by Avid and no part of it is to be disclosed to others without prior written permission from Avid.

Sponsor:	Name of Compounds:	Active Ingredient(s):
Avid Radiopharmaceuticals	 F-AV-1451([F-18]T807)	7-(6-[F-18]fluoropyridin-3-yl)-5H-pyrido[4,3-b]indole

Title of Study: F-AV-1451-A08

"F-AV-1451 PET Imaging in the Preclinical, Prodromal and Dementia Phases of Alzheimer's Disease"

# Planned number of subjects (Enrolled): Approximately 120

This study will be divided into the following groups:

- 1. Approximately 25 cognitively healthy control subjects with no memory complaints
- 2. Approximately 25 subjects with subjective memory complaints (SMC) and a negative amyloid scan
- 3. Approximately 25 subjects with subjective memory complaints (SMC) and a positive amyloid scan
- 4. Approximately 25 subjects with mild cognitive impairment (MCI)
- 5. Approximately 20 subjects with Alzheimer's disease (AD)

Subjects will be recruited from the pool of participants participating in the Australian Imaging Biomarker and Lifestyle study of Ageing (AIBL).

Name of compound and other imaging agents: F-AV-1451([F-18]T807)

Dose:

F-AV-1451 ([F-18]T807): 240 MBq + 10%

Route of Administration: Intravenous (IV) bolus

Study Phase: I

**Study Centers:** Approximately 1 center in Australia

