# 5.3 Selection of Subjects

#### 5.3.1 Inclusion Criteria

Subjects who meet the following criteria are eligible to enroll in this trial as cognitively healthy controls:

- 1. Met all eligibility criteria for this cohort in the AIBL study protocol; and
- 2. Consented and currently enrolled in the AIBL study protocol with amyloid PET conducted or planned and MRI, cognitive and amyloid PET scan data can be made available to this study.

Subjects who meet the following criteria are eligible to enroll in the arm of this trial reserved for subjects with subjective memory complaints:

- 1. Met all eligibility criteria for this cohort in the AIBL study protocol; and
- 2. Consented and currently enrolled in the AIBL study protocol with amyloid PET conducted or planned and MRI, cognitive and amyloid PET scan data can be made available to this study.

Subjects who meet the following criteria are eligible to enroll in the arm of this trial reserved for subjects with MCI:

- 1. Met all diagnostic and eligibility critiera for this cohort in the AIBL study protocol;
- 2. Consented and currently enrolled in the AIBL study protocol with amyloid PET conducted or planned and MRI, cognitive and amyloid PET scan data can be made available to this study; and
- 3. Have a reliable caregiver who is capable to provide correct information about the patient's clinical symptoms.

Subjects who meet the following criteria are eligible to enroll in the arm of this trial reserved for subjects with AD:

- 1. Met all diagnostic and eligibility criteria for this cohort in the AIBL study protocol;
- 2. Consented and currently enrolled in the AIBL study protocol with amyloid PET conducted or planned and MRI, cognitive and amyloid PET scan data can be made available to this study; and

3. Have a reliable caregiver who is capable to provide correct information about the patient's clinical symptoms.

Additionally, all subjects must meet all of the following criteria to be eligible to enroll in this trial:

- 1. Male or female English speaking subject > 60 years of age;
- 2. Have > 7 years of education;
- 3. Have adequate visual and auditory acuity to complete neuropsychological testing;
- 4. Can tolerate PET imaging procedures;
- 5. Can tolerate MRI scan procedures;

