# 7.1.1 Screening Visit:

Subjects currently enrolled in the AIBL (previously had amyloid imaging in the form of florbetapir (F) PET imaging) study will be contacted to participate. Screening may take place over several days. All screening assessments should be performed within 60 days of the initial F-AV-1451 PET imaging session.

Screening assessments will include:

- Informed Consent:
- Demographics (age, gender, race, ethnicity, education, alcohol, drug use and smoking);
- Medical history and concomitant medications;
- Physical and neurological examination;
- Disease history (date/months since symptom onset, date/months since diagnosis) for cognitively impaired subjects;
- Family history of neurologic disease;
- Safety assessments: Vital signs (pulse rate, respiratory rate, supine blood pressure, height and weight), ECG, and safety labs (hematology, chemistry and urinalysis); and
- A physician will see the subject during the screening visit.

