6.8 ADJUSTMENTS FOR COVARIATES

Analysis of Covariance (ANCOVA) models evaluating cognitive change in the exploratory analyses will be adjusted for the baseline value of the cognitive score, age, and years of education. Log-linear models estimating risk ratios in the exploratory analyses will be adjusted for the baseline value of the cognitive score, age, and years of education. ANCOVA models evaluating SUVr CFB in the exploratory analysis will be adjusted for baseline SUVr and age.

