7.3 ANALYSIS OF SCREENING AND BASELINE ASSESSMENTS

7.3.1 *Demographic and Other Baseline Characteristics*

All baseline summaries will be based on the safety population. Age (years), gender, amyloid status (A β +, A β -), tau status (AD-, AD+, AD++), race, ethnicity, height (cm), weight (kg), BMI, years of education, substance use (alcohol, smoking, and recreational drug history), MMSE, CDR-SB will all be reported in the demographics table using descriptive statistics.

All baseline cognitive scores are collected in the AIBL database. Baseline height and weight are the measurements collected on the AV-1451-A08 CRF.

7.3.2 *Medical and Surgical History*

Medical and surgical histories were coded using MedDRA version 17.0. Medical and surgical history will be defined in the same manner as in the protocol. Medical and surgical history will be presented for the safety population in a listing.

7.3.3 *Concomitant Therapy*

Concomitant therapies were coded using WHODRUG V20140601. Concomitant medications are medications that started prior to, on or after the informed consent date and ended on or after the date of the flortaucipir injection or were ongoing at the end of the study. Concomitant medications will be presented for the safety population in a listing.

7.3.4 *Physical Examination*

Physical examination will be summarized for the safety population. Each assessment of the physical examination – general appearance, skin, HEENT, respiratory, cardiovascular, gastrointestinal, musculoskeletal – will be summarized in a table in aggregate and by diagnosis.

Individual subject assessments will be presented in a listing, including any abnormalities noted on the CRF.

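### SAP 6.4 derives age by subtracting calendar years, which prints one year above age at last birthday for every subject whose birthday falls after the consent date

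*SAP*

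**What the plan says.** SAP 6.4 gives the whole rule in one sentence: "Age will be derived in years as the difference between the year of informed consent and year of birth". Month and day play no part.

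The variable is used in two places. SAP 7.3.1 lists age in years among the baseline characteristics that "will all be reported in the demographics table using descriptive statistics". SAP 6.8 makes it a covariate in the exploratory models: the cognitive-change ANCOVAs and the log-linear risk-ratio models "will be adjusted for the baseline value of the cognitive score, age, and years of education", and "ANCOVA models evaluating SUVr CFB in the exploratory analysis will be adjusted for baseline SUVr and age". The partial correlations in SAP 7.4.2.8 and 7.4.2.9 also adjust for age.

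On the protocol side, the entry criterion in 5.3.1 is "Male or female English speaking subject > 60 years of age", and the screening items in 7.1.1 begin "Demographics (age, gender, race, ethnicity, education, alcohol, drug use and smoking". Neither document says whether the over-60 limit refers to exact or completed age, whether a full date of birth is recorded, or whether the screening age is a field of its own.

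**The concern.** A whole-number age in a demographics table will normally be read as age at last birthday. The SAP rule gives that value only to subjects whose birthday has been reached by the consent date. It gives everyone else one year more, so the error runs in one direction against that convention.

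The value also depends on when in the year a subject consents. Take two subjects who are both exactly 70.5 years old at consent in year Y. One consents in mid-January, was born in mid-July of Y − 71, and prints as 71. The other consents in mid-December, was born in mid-June of Y − 70, and prints as 70.

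At stake are the accuracy of the reported ages, the use of those ages to show afterwards that the sample met the age limit, and, in principle, the quality of a covariate.

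**Working it through.** **Inputs from the documents.** The rule (SAP 6.4); planned enrolment, "Planned number of subjects (Enrolled): Approximately 120" (protocol synopsis); the age limit (Protocol 5.3.1). The documents state no mean age, age SD or consent dates, so there is no figure to reproduce.

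**Assumptions.** Let u be the consent date and v the birthday, each as a fraction of the year. The base case takes u and v as independent and uniform. The boundary shares in step 4 assume normally distributed ages with mean 73 and SD 6. The covariate check in step 5 uses an age SD of 5 to 8. The closed forms below were checked with 2,000,000 simulated subjects.

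**1. Against age at last birthday.** The excess is 1 if v > u and 0 otherwise. In the base case P(v > u) = 0.50, so the mean excess is 0.50 year. In 120 subjects the expected number one year too old is 120 × 0.50 = 60, with SD √(120 × 0.25) = 5.5 and a 95% range of 60 ± 1.96 × 5.5, about 49 to 71.

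**2. Sensitivity to consent timing.** With uniform birthdays the share at +1 is 1 − mean(u). This is also the mean excess in years.

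| Consent confined to | Share at +1 |
|---|---|
| January | 1 − 1/24 = 0.96 |
| First quarter | 1 − 1/8 = 0.875 |
| First half | 0.75 |
| Second half | 0.25 |
| Fourth quarter | 1 − 7/8 = 0.125 |
| December | 1 − 23/24 = 0.04 |

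**3. Against exact age.** The error is v − u. In the base case its mean is 0 and its SD is √(1/12 + 1/12) = √(1/6) = 0.41 year. Completed years has mean error −0.50 and SD √(1/12) = 0.29 year. The year difference therefore has twice the error variance of completed years.

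**4. At the age limit.**
- A derived age of 61 or more always means an exact age above 60. The extreme case is a birthday on 31 December with consent on 1 January, which gives 60 years and one day.
- A derived age of 60 covers exact ages from just over 59 to just under 61. Under the assumed age distribution about 44% of these are below 60.
- A completed age of 60 prints as 61 in about half of cases (53% in the simulation).

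**5. As a covariate.** Reliability against exact age is SD²/(SD² + 1/6).
- Age SD 5: 25/25.167 = 0.993.
- Age SD 8: 64/64.167 = 0.997.
- With 1/12 in place of 1/6, for completed years: 0.997 and 0.999.
- The correlation between the two versions of age is 0.995 to 0.998.

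**The case against.** The strongest reply is that this is a convention, not an error. The rule is prespecified, reproducible and the same for every group. Against exact age it has no mean bias when consent dates are evenly spread, whereas completed years is half a year low. The primary analyses do not use age: the two-way ANOVA in SAP 7.4.1.1 has cognitive group and amyloid status as its effects, and the CMH test in 7.4.1.2 controls for amyloid status. Nor do the documents show that a full date of birth is held.

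Most of that stands, and it limits the point. It does not remove it. Readers of a demographics table will take age in whole years as completed years, and on that reading the shift is systematic. Even against exact age the rule is noisier than the usual derivation. The SAP gives no reason for dropping to calendar years, although it works with full dates elsewhere (relative days in 6.7, the consent date in 7.3.3).

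A reader might also infer that the rule hides breaches of the entry criterion. The documents do not support that as a general statement. If the limit means exact age above 60, no one at or below 60 can print as 61 or more, and a 59-year-old printed as 60 still does not appear to meet it. A breach could be masked only if the limit means a completed age of at least 61, and Protocol 5.3.1 does not say so. Neither document says eligibility is judged from the SAP-derived age; it is an entry criterion, and age is listed as a screening item.

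**Conclusion.** The point holds as a minor reporting matter. For every subject whose birthday falls after consent, the SAP rule prints one year above age at last birthday.

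The figures of about half of subjects and about 0.5 year carry two conditions: evenly spread consent dates, and completed years as the comparator. With other consent patterns the share could lie anywhere from about 4% to 96%.

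A reader might infer that study results are affected. They are not, to any degree that matters: covariate reliability stays above 0.99 for any age SD in the assumed range, and age is absent from the primary analyses. For the over-60 limit, the supportable statement is that the derived age cannot reliably confirm the rule near the boundary, not that ineligible subjects were admitted or concealed.

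**What to change.** Replace SAP 6.4 with age in completed years from full date of birth to date of informed consent, where both are held, and use it in the demographics table and the age-adjusted models. If a full date of birth is not held, use the age recorded at screening (Protocol 7.1.1). If birth year is all that is available, keep the subtraction but label the variable as a calendar-year difference in the table and state that it can exceed age at last birthday by one year. In that last case, do not use it to verify the age limit.

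Where the dates are held, the cost is one line of SAP text and one line of code. Where they are not, it is a table label and a footnote. The case report form, which would settle which applies, is not among the documents.

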6.5 CALCULATING YEARS OF EDUCATION

Years of education will be derived using the following mapping based on the 'Highest Level of Education' collected on the demographics case report form (CRF).

- Elementary School = 6
- Middle School = 8
- High school = 12
- College/University = 16
- Post Graduate School = 18

Any 'Other' response clarified in the CRF where a definitive number of years can be determined (e.g. '2 years of college' or '14 years') will be mapped accordingly based on the definitions bulleted above. Otherwise, 'Other' will be mapped to the mean value of available data based on the aforementioned mapping.

6.6 CALCULATING BMI

Body Mass Index (BMI) will be calculated using the following formula.

$$BMI = \frac{weight \ (kg)}{height^2(m^2)}$$

6.7 TIME POINT ALGORITHMS

The date of first dose of flortaucipir will be considered relative day 1, and the day before the first dose of study drug will be relative day -1. Relative days will be calculated as follows only when the full assessment date is known (i.e., partial dates will have missing relative days):

For days on or after the first dose of study drug:

Date of Assessment – Date of First Dose of Study Drug + 1.

For days before the first dose of study drug:

Date of Assessment – Date of First Dose of Study Drug.

6.8 ADJUSTMENTS FOR COVARIATES

Analysis of Covariance (ANCOVA) models evaluating cognitive change in the exploratory analyses will be adjusted for the baseline value of the cognitive score, age, and years of education. Log-linear models estimating risk ratios in the exploratory analyses will be adjusted for the baseline value of the cognitive score, age, and years of education. ANCOVA models evaluating SUVr CFB in the exploratory analysis will be adjusted for baseline SUVr and age.

6.9 HANDLING OF DROPOUTS OR MISSING DATA

Dropout subjects will not be replaced in this study. The missing data will not be imputed.

6.10 MULTI-CENTER STUDIES AND POOLING OF CENTERS

The data from all centers will be pooled. The pooled data will be analyzed and presented.

6.11 MULTIPLE COMPARISONS/MULTIPLICITY

No multiple comparisons/multiplicity adjustment is planned. Unless otherwise specified, hypothesis testing will be two-sided with type I error rate of 0.05.

7 STATISTICAL ANALYSIS

7.1 ANALYSIS POPULATIONS

7.1.1 Enrolled Population

The enrolled population will consist of all enrolled AIBL subjects who have baseline cognitive assessments captured in the AIBL clinical database, and who signed informed consent for the AV-1451-A08 protocol. Disposition information will be summarized using the enrolled population.

7.1.2 Safety Population

The safety population will consist of all subjects that received an injection of flortaucipir. All baseline information and safety endpoints will be reported on using the safety population.

7.1.3 Efficacy Population

The efficacy population used in the primary analysis will include all subjects in the safety population with a valid interpretable baseline PET image (SUVr and/or visual read) available. The exploratory efficacy population will include all subjects with available SUVr, flortaucipir visual read, and the relevant clinical/cognitive assessment.

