3 STUDY DESIGN

3.1 GENERAL DESIGN

This is a phase I study that will evaluate imaging characteristics of flortaucipir in the preclinical, prodromal and dementia phases of AD.

AIBL subjects who have previously had beta-amyloid imaging in the form of florbetapir PET imaging will be contacted to participate and must provide informed consent before starting any 18F-AV-1451-A08 study procedures. In addition to consenting to study procedures, participants will consent to have amyloid PET images and data, MRI images and data, and cognitive data made available to this study to allow analysis and comparison. Other AIBL participants who have had other types of amyloid imaging will be recruited when required to reach the study target enrollment numbers. Screening assessments may take place over several days and will include demographic information and safety assessments.

Subjects who qualify for the study will return to the clinic at a later date for a flortaucipir PET scan. To optimally compare to the AIBL cognitive evaluation, the flortaucipir scan will be obtained within +/- 2 months of the planned (or obtained) cognitive evaluation in AIBL.

Subjects will have a follow-up flortaucipir PET scan at 12 (+/- 3) months following the initial flortaucipir scan. A brief cognitive evaluation will be performed on the day of the follow-up flortaucipir scan or on a separate visit within 2 months of the follow-up scan.

Table 2: Trial Flow Chart

Evaluations	Screening Visit	MRI Visit	Flortaucipir Imaging Visit	Follow-up Flortaucipir Imaging Visit	Follow-Up Phone Call
Demographics	X				
Medical History	X				
Concomitant Medications	X				X
Physical Examination	X				
Neurological Examination	X				
ECG	X				
Safety Labs ^a	X				
Vital Signs	X		X	X	
Neurological Testing			X	X	
MRI of the Brain		X			
PET Brain Scan			X		
Follow-up Phone Call					X
Evaluation by Physician/Designee	X		X	X	
Adverse Events	X	X	X		X
Serious Adverse Events	X	X	X		X

^aSafety labs to be collected any time between consent and flortaucipir injection at Imaging Visit

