3.1.3.2 Initial flortaucipir PET Imaging Visit

The initial flortaucipir PET scan was obtained within +/- 2 months of the planned (or obtained) cognitive evaluation in AIBL.

A physician must have seen the subject prior to the administration of the flortaucipir injection to determine if they were suitable to undergo the scan, and again prior to discharge from the imaging center to evaluate the subject's readiness for discharge. Vital signs were taken (pulse rate, respiratory rate, and supine blood pressures) immediately prior to the administration of flortaucipir and prior to discharge. Weight was also collected, prior to injection.

A 5 minute brain scan began immediately following the administration of flortaucipir, and another continuous 30-minute brain scan approximately 75 minutes after injection.

Adverse events were continuously monitored during the flortaucipir PET imaging visit. A follow-up phone call to the subject, or designated decision maker, was conducted within 2 or 3 business days of the imaging day, but not before 48 hours post-injection, to confirm subject well-being and to collect information about any new adverse events.

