7.4.2.1 Two-way ANOVA for Comparison of MUBADA SUVr between Amyloid Groups

Depending on available data, the same analyses as described in Section 7.4.1.1 will be performed with the substitution of comparing MUBADA SUVr between amyloid groups (A β + vs. A β -) rather than cognitive groups, via properly set up contrasts.

7.4.2.2 ANCOVA for Comparison of MMSE CFB as a Function of Tau Scan Visual Interpretation

The objective of this analysis is to determine if baseline tau status will predict subjects' cognitive deterioration.

The first hypothesis will test whether a difference in MMSE CFB exists between AD++ and Non-AD++ (AD- and AD+ only) subjects at 12 month follow-up visit.

The second hypothesis will test whether a difference in MMSE CFB exists between subjects with AD pattern (AD+ and AD++) and AD- subjects.

The third hypothesis will test whether a difference in MMSE CFB exists between AD++ and AD- subjects.

Depending on available data, an ANCOVA model with MMSE CFB at 12 months as the dependent variable, adjusted for baseline MMSE, age, cognitive group, level of education, and the interaction of cognitive group and tau status will be used to test these hypotheses. The appropriate contrasts will be set up to test each hypothesis.

Descriptive summary statistics for MMSE at baseline, 12 months and CFB will be summarized for all subjects by tau status (AD-, AD+, AD++). Group LSM, the difference in LSM between groups, and the p-values from each ANCOVA contrast will be included in the table.

A scatter plot will be created to display the relationship between MMSE CFB and baseline MUBADA SUVr across each tau group.

7.4.2.3 ANCOVA for Comparison of CDR-SB CFB as a Function of Tau Scan Visual Interpretation

The same analyses as described in Section 7.4.2.2 will be performed with the substitution of CDR-SB for MMSE.

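### The exploratory set requires both SUVr and a visual read although the models use one or the other, and the enrolled set is not guaranteed to contain every dosed subject.

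*SAP*

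**What the plan says.** SAP 7.1.3 gives two efficacy rules side by side. The primary set takes safety-population subjects with a "valid interpretable baseline PET image (SUVr and/or visual read) available". The next sentence is stricter: "The exploratory efficacy population will include all subjects with available SUVr, flortaucipir visual read, and the relevant clinical/cognitive assessment". The qualifier on relevance attaches to the clinical or cognitive assessment only; nothing limits the SUVr or the read to analyses that use them. SAP 6.9 rules out imputation.

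For the amyloid comparison, SAP 7.4.2.1 says that "the same analyses as described in Section 7.4.1.1 will be performed with the substitution of comparing MUBADA SUVr between amyloid groups".

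On the wider populations, SAP 7.1.1 states: "The enrolled population will consist of all enrolled AIBL subjects who have baseline cognitive assessments captured in the AIBL clinical database", together with signed consent for this protocol. SAP 7.1.2 sets no cognitive condition: "The safety population will consist of all subjects that received an injection of flortaucipir". SAP 7.2 builds the disposition table on the enrolled set and has it summarise the analysis populations and the discontinuations. On timing, SAP 3.1.3.2 states: "The initial flortaucipir PET scan was obtained within +/- 2 months of the planned (or obtained) cognitive evaluation in AIBL".

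**The concern.** An analysis set should hold the subjects who have the variables that the analysis needs. Here a subject with a valid SUVr but no read is removed from correlations and t-tests that never use a read, and a subject with a read but no SUVr is removed from risk ratios that never use SUVr. The SAP gives no reason for this. Two contrasts from one two-way ANOVA may also be estimated on two different sets of subjects, so the two tables need not agree on N, residual variance or least squares means.

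The enrolled set has a different problem. It is normally the outermost population, with the safety and efficacy sets inside it. A rule that depends on a record held in another study's database does not guarantee this. The subject most at risk of omission is one who leaves early, whom a disposition table is meant to show.

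**Working it through.** There is no power or sample-size figure to reproduce: SAP 3.3 and protocol 8.2 say that the sample size had no statistical basis. The planned group sizes do add up: 25 + 25 + 25 + 25 + 20 = 120.

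**Exploratory set: what each analysis uses (SAP 7.4.2)**

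- 7.4.2.1: SUVr, cognitive group and amyloid status. No read.
- 7.4.2.2-3: change in MMSE or CDR-SB by visual read, with covariates. SUVr appears only in the accompanying scatter plot.
- 7.4.2.4-5: the same models with impairment group in place of tau status. Neither imaging measure is the comparison factor.
- 7.4.2.6-7: visual read, dichotomised cognitive change and covariates. No SUVr.
- 7.4.2.8-9: SUVr (or its change) and cognitive change. No read. The cross-reference in 7.4.2.9 points to itself; I take it to mean 7.4.2.8.
- 7.4.2.10: SUVr change within amyloid group. No read.

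None of these models has both measures in it; only the scatter plots by tau group need both.

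**7.4.2.1 against 7.4.1.1.** The model is the same: baseline MUBADA SUVr on cognitive group and amyloid status. Under the primary rule, the fit uses everyone with an SUVr and those two factors, because a subject with only a read has no dependent variable and drops out anyway. Under the exploratory rule, the fit uses the same subjects minus those without a read. The two fits therefore differ by exactly the subjects who have an SUVr and no read.

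**Size.** The documents give no missingness rates, so let f be the assumed share of 120 subjects with only one measure. The rest are taken to have both, with loss proportional across groups. The worst case for a given analysis is that all of these subjects have the measure it needs. Then n falls from 120 to 120(1 - f), and the standard error rises by 1/sqrt(1 - f) - 1:

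- f = 0: n = 120, rise 0%
- f = 3%: n = 116.4, rise 1.5%
- f = 5%: n = 114, rise 2.6%
- f = 10%: n = 108, rise 5.4%

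If instead each measure is missing independently at rate m, an analysis-specific set keeps 120(1 - m) and the joint rule keeps 120(1 - m)²:

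- m = 1%: 118.8 against 117.6, rise 0.5%
- m = 10%: 108.0 against 97.2, rise 5.4%

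If the same scans fail both measures, the joint rule costs nothing.

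**Enrolled set**

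1. The safety set requires an injection only (SAP 7.1.2).
2. The enrolled set requires consent and a captured AIBL baseline cognitive assessment (SAP 7.1.1).
3. The scan may come up to 2 months before an AIBL evaluation that is only planned (SAP 3.1 and 3.1.3.2; protocol 5.1 and 7.1.3). Inclusion asks only that AIBL cognitive data can be supplied (protocol 5.3.1).
4. A subject can therefore consent, be dosed and miss that evaluation. If no earlier AIBL score counts as baseline, this subject is in the safety set, and in the primary efficacy set if the image is valid, but not in the enrolled set.
5. With 120 dosed and k such subjects, the disposition table rests on 120 - k. For example, k = 3 gives 117 against 120 in the safety tables.
6. Protocol 8.6 wants every early discontinuation listed and the reasons tabulated. A table limited to the enrolled set would leave out the reasons for these k subjects if they discontinued. SAP 4.2 declares no change on this point.

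**The case against.** The strongest reply is that nothing need be lost. SUVr and read come from the same baseline image, so a failed scan probably fails both. The either-or wording for the primary set may only reflect that the primary analysis has a quantitative and a qualitative part; it does not show that the sponsor expects subjects with one measure. A common complete-case set is also a recognised choice that keeps N comparable across tables, and the plots in 7.4.2.2-3 do use both measures. The wording of 7.4.2.1 can be read as carrying over the primary set. All of this stands as a limit on size. It does not change the literal rule, which requires a read for analyses that do not use one.

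A reader might infer that 7.4.2.1 also requires an MMSE or CDR-SB score, which would make the loss larger. The text does not support this: only the relevant assessment is required, and neither score is in that model. Any mismatch comes from the read requirement alone.

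A reader might also infer that early dropouts disappear from the report. That goes too far. They stay in the safety set, and in the primary efficacy set if the image is valid; protocol 8.6 still requires them to be listed; and SAP 7.2 adds a disposition listing. Participants are existing AIBL members, so an earlier AIBL score might meet SAP 7.1.1, and leaving this study does not by itself mean leaving AIBL. However, SAP 6.2 and 6.3 set no window for the baseline score, so the SAP does not settle the matter.

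**Conclusion.** The point holds as a small defect in two stated rules.

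First, the single exploratory set can only lose usable subjects, and it can separate 7.4.2.1 from its parent ANOVA. The size is unknown and may be nil: about 0-5% on standard errors if 0-10% of subjects had only one measure, a range that is assumed and not taken from the documents.

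Second, the safety and primary efficacy sets are not guaranteed to nest within the enrolled set. If a dosed subject lacks the AIBL baseline score and no earlier score counts, the disposition table is short by that subject. If that subject also discontinued, the table conflicts with protocol 8.6. The effect is on disposition counts, not on the safety or primary efficacy results.

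The documents do not show that any subject is in fact affected by either rule.

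**What to change.** - In SAP 7.1.3, define the exploratory set per analysis as safety-population subjects with the variables in that model, naming the visit for SUVr.
- In SAP 7.4.2.1, state that the amyloid contrast comes from the same subjects and the same fit as 7.4.1.1.
- In SAP 7.1.1, define enrolled as all subjects who signed consent for this protocol, so that the safety and efficacy sets nest within it. Availability of the AIBL baseline score can be shown as a row in the disposition table.

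The cost is a few sentences in the SAP and no new data. N will vary slightly between exploratory tables and should be shown in each.
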